#### 3.1.5 Prior Therapy

There is no limit to the number of prior therapies.

#### 3.1.6 Informed Consent/Assent

All subjects must have the ability to understand and the willingness to sign a written informed consent.

### 3.2 Exclusion Criteria

- 3.2.1 Patient has anti-HLA antibodies specific for HLA antigens expressed by the HB1.F3.CD NSCs.
- 3.2.2 Patient has not recovered from any toxicity of prior therapies. An interval of
  - 3.2.2.1 At least 6 weeks must have elapsed since taking a nitrosourea-containing chemotherapy regimen.

- 3.2.2.2** At least 4 weeks since completing a non-nitrosourea-containing cytotoxic chemotherapy regimen (except temozolomide: only an interval of 23 days is required from the last dose administered when patient has been recently treated with the standard temozolomide regimen of daily for 5 days, repeated every 28 days).
- 3.2.2.3** At least 2 weeks from taking the last dose of a targeted agent.
- 3.2.2.4** At least 4 weeks from the last dose of bevacizumab.
- 3.2.3** Patient is unable to undergo an MRI.
- 3.2.4** Patient is allergic to 5-FC, leucovorin, or 5-FU.
- 3.2.5** Patient has chronic or active viral infections of the CNS.
- 3.2.6** Patient has a coagulopathy or bleeding disorder.
- 3.2.7** Patient has an uncontrolled illness including ongoing or active infection.
- 3.2.8** Patient is receiving any other investigational agents, or concurrent biological, chemotherapy, or radiation therapy.
- 3.2.9** Patient has had prior therapy with neural stem cells.
- 3.2.10** Patient is pregnant or breast feeding. Pregnant women are excluded from this study because 5-FC and leucovorin are agents with the potential for teratogenic or abortifacient effects. Because there is an unknown but potential risk for adverse events in nursing infants secondary to treatment of the mother with 5-FC and leucovorin, breastfeeding should be discontinued if the mother is participating in this study.
- 3.2.11** Patient has another active malignancy.
- 3.2.12** Non-compliance

A patient has a serious medical or psychiatric illness that could, in the investigator's opinion, potentially interfere with the safety monitoring requirements and completion of treatment according to this protocol.

### **3.3 Inclusion Criteria for Proceeding to Treatment with 5-FC**

- 3.3.1** Patient must be tolerating oral intake.
- 3.3.2** A patient's daily total dose of dexamethasone must be  $\leq 16$  mg by day 4.

### **3.4 Inclusion of Women and Minorities**

The study is open anyone regardless of gender or ethnicity. Efforts will be made to extend the accrual to a representative population, but in a trial which will accrue approximately 18-21 subjects, a balance must be struck between subject safety considerations and limitations on the number of individuals exposed to potentially toxic or ineffective treatments on the one hand and the need to explore gender, racial, and ethnic aspects of clinical research on the other. If differences in outcome that correlate to gender, racial, or ethnic identity are noted, accrual may be expanded or additional studies may be performed to investigate those differences more fully.

---

## **4.0 Screening and Registration Procedures**

### **4.1 Screening Procedures**

Diagnostic or laboratory studies performed exclusively to determine eligibility for this trial will be done only after obtaining written informed consent. Studies or procedures that were for clinical indications (not exclusively to determine study eligibility) may be used for baseline values, even if the studies were done before informed consent was obtained. Reference is made to Section 10.0 – Study Calendar.

#### **4.2 Informed Consent**

The investigational nature and objectives of the trial, the procedures and treatments involved and their attendant risks and discomforts, and potential alternative therapies will be carefully explained to the subject and a signed informed consent will be obtained. Documentation of informed consent for screening will be maintained in the subject's research chart and medical record.

#### **4.3 Registration Requirements/Process**

Registration of participants is to be via completion of the following steps:

- 4.3.1** Prospective participants must complete the informed consent process, including a signed informed consent, prior to proceeding to study screening.
- 4.3.2** Screening procedures and windows are detailed in Section 10 and Table 10, Study Activity Calendar.
- 4.3.3** A study specific eligibility checklist developed by the Clinical Trials Office at the City of Hope will be used to facilitate confirmation that a prospective participant meets all eligibility criteria.
- 4.3.4** Once all the pre-study requirements have been fulfilled, including a completed eligibility checklist, the study coordinator can register the eligible patient into MIDAS.
- 4.3.5** Patients failing to meet all protocol eligibility criteria, including informed consent, may not be registered for the trial.

#### **4.4 Dose Level Assignment**

Please see section 5.7.

## 5.0 Treatment Program

### 5.1 Treatment Overview

#### Dose Escalation Schema

Dose Level	Neural Stem Cells (i.c. on days 1 & 15)	5-FC (mg/kg q 6h p.o. on days 4-10 & 18-24)	Leucovorin (mg q 6h p.o. on days 4-10 & 18-24)	Initial Enrollment	If 1 DLT, additional enrollment
-1 a	$3.75 \times 10^7$	28	---	3	3
1	$5 \times 10^7$	37.5	---	3	3
2	$1 \times 10^8$	37.5	---	3	3
3	$1.5 \times 10^8$	37.5	---	3	3
4 b,c	Highest tolerated dose combination of 5-FC and NSCs		25	3	3

aIf a DLT is observed in 2 or more patients at dose level 1, then a de-escalation dose, **dose level -1** will be tested. With dose level -1, the doses of NSCs and 5-FC will both be reduced by 25%; however, if the DLT can clearly be attributed only to 5-FC, then only the dose of 5-FC will be reduced by 25% (likewise for the NSCs if the DLT is clearly attributable to only the NSCs) for dose level -1.

bIf the addition of leucovorin to the highest tolerated dose combination of 5-FC and NSC requires a dose de-escalation, then leucovorin will be discontinued and the MTD/MFD will be the highest tolerated dose combination of 5-FC and NSCs without leucovorin. A total of 6 patients will be treated at the maximum tolerated dose (MTD), or if the MTD is not reached, at the maximum feasible dose (MFD).

cDose level 4 patients will undergo intracerebral microdialysis to measure NSC-mediated conversion of 5-FC to 5-FU.

**Cycle 1a****Day 1**

- Tumor resection or biopsy is performed.
- HB1.F3.CD NSCs are administered intracranially.
- A Rickham catheter is placed.
- Dose level 4 patients only: a microdialysis catheter is placed.

**Days 4-10**

- Patients take 5-FC 37.5 mg/kg p.o. q 6h.
- Patients on dose level 4 also take leucovorin 25 mg p.o. q 6h.
- Dose level patients only: serial dialysate and blood samples collected.

**Days 15**

- HB1.F3.CD NSCs administered intracranially via the Rickham catheter.
- Blood drawn for immunologic correlative studies.

**Days 18-24**

- Patients take 5-FC 37.5 mg p.o. q 6h.
- Patients on dose level 4 also take leucovorin 25 mg p.o. q 6h.

a The length of a treatment cycle is 28 days. After cycle 1, the NSCs will be administered via the Rickham catheter on days 1 and 15 of a cycle. The 5-FC (and leucovorin for dose level 4 patients) will continue to be administered on days 4-10 and 18-24. Blood draws for immunologic correlative studies will be done on days 1 and 15 of cycle 2, and then only on day 15 of subsequent cycles. A brain MRI will be performed after every 2 cycles of treatment.

## 5.2 Treatment Plan for Cycle 1

**5.2.1 Pre-surgery, post-registration: Pre-surgical planning MRI** A pre-surgical planning post-registration MRI may be performed if indicated by the neuro-surgeon.

### 5.2.2 Cycle 1 Day 1: Intracerebral administration of NSCs during surgery

All study patients must have confirmation of recurrent tumor documented on frozen section at the time of surgery before proceeding with direct intracerebral injection of the NSCs.

The maximum concentration of NSCs is  $6.7 \times 10^7$ /ml (or  $1 \times 10^8/1.5$  ml).

#### 5.2.2.1 Patients who undergo a craniotomy for tumor removal:

When the study neurosurgeon has finished resecting tumor, he will directly inject CD-expressing NSCs into the brain tissue of the resection cavity.

**Dose level -1 (if a decision is made to dose reduce the NSCs):**  $3.75 \times 10^7$  NSC will be suspended in 0.6 ml of 2% human serum albumin (HSA)/artificial CSF (Perfusion Fluid CNS; ref no. P000151, M Dialysis, Solna, Sweden).

**Dose level 1:**  $5 \times 10^7$  NSCs will be suspended in 0.75 ml of 2% HSA/artificial CSF.

**Dose level 2:**  $1 \times 10^8$  NSCs will be suspended in 1.5 ml of 2% HSA/artificial CSF.

**Dose level 3:**  $1.5 \times 10^8$  NSCs will be suspended in 2.25 ml of 2% HSA/artificial CSF.

**Dose level 4:** As per dose level 3.

The total dose of NSCs will be injected in divided 100-150  $\mu$ l volumes, as evenly spaced as possible, throughout the wall of the resection cavity; administering them only into areas that are surgically safe and feasible. The NSCs will be injected 2.5 cm deep and tracked up to approximately 1 cm deep, (slowly injecting as the needle is withdrawn, so as to distribute the NSCs from 2.5 cm – 1 cm depth).

**After the NSCs have been administered, a 9.5 mm Rickham reservoir attached to an open-ended catheter (a Rickham) will be placed** in residual tumor tissue or peritumoral tissue to deliver subsequent doses of NSCs.

A post-operative MRI of the brain will be done on day 2 to serve as a baseline scan with which to compare subsequent MRIs.

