#### **5.4.1.1 Patients who undergo a craniotomy for tumor removal**

Once the study neurosurgeon has finished resecting as much tumor as safely possible, he will insert a 70 Brain MD Catheter (membrane length 10 mm; shaft length 100 mm, ref. no. P000050, M Dialysis, Solna, Sweden) in residual tumor or within 5-15 mm of the resection cavity. If feasible a second catheter will be added to a different geographic location.

The NSCs will then be injected. **At the margin of the catheter location, 2-4 of the 100-150  $\mu$ l aliquots of NSCs will be injected.** The total dose of NSCs, ( $1.5 \times 10^8$ )—will be administered as per section 5.2.2.1.

After the NSCs have been administered, a Rickham will be placed in residual tumor or peritumoral tissue to deliver subsequent doses of NSCs.

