#### **5.4.1.2 Patients who undergo a stereotactic brain biopsy**

After performing the tumor biopsy, a 70 Brain MD Catheter will be passively introduced into the injection site through the biopsy track. If feasible, a second MD catheter will be added to a different geographic location. The study neurosurgeon will then place the Rickham through the same biopsy track, and the dose of NSCs ( $1.5 \times 10^8$ ) will then be administered through the Rickham catheter as per section 5.2.2.2

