## 5.6 Study Design

The study will implement a standard 3+3 design. The goal will be to determine the maximum tolerated dose (MTD), which is defined as the highest dose level tested in which fewer than 33% of patients experienced a DLT attributable to the treatment regimen of NSCs with 5-FC and leucovorin, when at least 6 patients were treated at that dose and are evaluable for toxicity. If the MTD has not been reached with 1.5 x 108 NSCs, 37.5 mg/kg q6h 5-FC and 25 mg q6h leucovorin (dose level 3 plus leucovorin), then that dose will be termed the maximum feasible dose (MFD).

- 5.6.1** Phase I cohorts will be of 3 or 6 participants, as indicated by the dose-escalation criteria.
- 5.6.2** The dose schedule is provided in the table in section 5.7. The first cohort of patients will start at dose level 1.
- 5.6.3** Dose escalation will proceed through the identified doses without skipping any dose levels.
- 5.6.4** *Enrollment of the first 3 patients to dose levels 1-3 will be staggered* by requiring that each of the first 3 patients be separately observed for 4 weeks (or until the DLT assessment period has ended) before the next patient can start treatment on that dose level.
- 5.6.5**
- 5.6.6** Dose escalation rules:
  - 5.6.6.1 If 0/3 study participants experiences a DLT, the next cohort of 3 study patients will be treated at the next higher dose level.
  - 5.6.6.2 If 1/3 study participants experiences a DLT, the cohort will be expanded by another 3 study participants who will be treated at the same dose level for a total of 6 study participants.
  - 5.6.6.3 If 1/6 participants experiences a DLT, the next cohort of 3 study participants will be treated at the next higher dose level.
  - 5.6.6.4 If 2 or more participants of either a 3 participant or 6 participant cohort encounter a DLT, then the MTD has been exceeded. If applicable, three (more) participants will be enrolled at the next lower dose level.
  - 5.6.6.5 At least 6 patients will be treated at the MTD (or MFD, if the MTD is not reached).

For a patient to be counted for dose escalation, s/he must receive at least 80% (+/- 5%) of the assigned NSCs on days 1 and 15 and 80% (+/- 5%) of the 5-FC (and leucovorin, as indicated) on days 4-10 and 18-24 during cycle 1 and be followed up to and including cycle 2 day 1 safety assessments or have experienced a DLT.

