## 5.7 Dose Escalation Schema

Dose Level	Neural Stem Cells (i.c. on days 1 & 15)	5-FC (mg/kg q 6h p.o. on days 4-10 & 18-24)	Leucovorin (mg q 6h p.o. on days 4-10 & 18-24)	Initial Enrollment	If 1 DLT, additional enrollment
------------	---	---	--	--------------------	---------------------------------

-1 a	$3.75 \times 10^7$	28	---	3	3
1	$5 \times 10^7$	37.5	---	3	3
2	$1 \times 10^8$	37.5	---	3	3
3	$1.5 \times 10^8$	37.5	---	3	3
4 b,c	Highest tolerated dose combination of 5-FC and NSCs		25	3	3

aIf a DLT is observed in 2 or more patients at dose level 1, then a de-escalation dose, **dose level -1** will be tested. With dose level -1, the doses of NSCs and 5-FC will both be reduced by 25%; however, if the DLT can clearly be attributed only to 5-FC, then only the dose of 5-FC will be reduced by 25% (likewise for the NSCs if the DLT is clearly attributable to only the NSCs) for dose level -1.

bIf the addition of leucovorin to the highest tolerated dose combination of 5-FC and NSC requires a dose de-escalation, then leucovorin will be discontinued and the MTD/MFD will be the highest tolerated dose combination of 5-FC and NSCs without leucovorin. A total of 6 patients will be treated at the maximum tolerated dose (MTD), or if the MTD is not reached, at the maximum feasible dose (MFD).

cPatients on dose level 4 will undergo intracerebral microdialysis to measure NSC-mediated conversion of 5-FC to 5-FU.

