### 7.2 Monitoring and Personnel Responsible for Monitoring

The City of Hope Protocol Management Team (PMT) consisting of the PI, collaborating investigators, CRA, protocol nurse, and statistician is responsible for monitoring the data and safety of this study, including implementation of the stopping rules for safety.

This study will utilize the Phase I tracking log to monitor data and safety for dose escalation, recording doses administered and resultant adverse events. The tracking log will contain dose levels administered, DLT-defining adverse events, and documentation that the data from a dose level is complete before dose escalation. Those data and safety elements will be reported to the COH DSMC as applicable with the PMT report, which will be submitted quarterly from the anniversary date of activation, as noted in Table 1 below. Protocol specific data collection will include the following items: adverse events per dose level, patient outcomes, and protocol deviations.

A decision to escalate to the next dose level will be made by the PMT only after all patients on the current dose level have been observed through day 28. Enrollment of the first 3 patients to dose levels 1-3 will be staggered by requiring that each of these patients be observed for 28 days before the next patient can begin treatment on a particular dose level.

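### The level 4 stem cell dose is stated in two ways, which disagree if level 2 or level 3 is not tolerated

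*Combined protocol and SAP*

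**What the plan says.** The dose escalation tables, including those in 5.1 and 5.7, define the NSC and 5-FC part of level 4 as "Highest tolerated dose combination of 5-FC and NSCs" and add leucovorin 25 mg every 6 hours. Footnote b to the table describes level 4 in the same way. Section 4.4 sends dose level assignment to that table ("Please see section 5.7").

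Section 5.6.6.4 gives the failure rule: "If 2 or more participants of either a 3 participant or 6 participant cohort encounter a DLT, then the MTD has been exceeded". Section 5.6 mentions 1.5 × 10^8 NSCs with leucovorin only for the case where the MTD has not been reached ("dose level 3 plus leucovorin), then that dose will be termed the maximum feasible dose (MFD").

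The administration sections read differently. For level 4, sections 5.2.2.1 (craniotomy, day 1), 5.2.2.2 (biopsy, day 1) and 5.2.5 (day 15) each say "As per dose level 3". Section 5.4 is restricted to level 4 patients, and it prints the number. In 5.4.1.1: "The total dose of NSCs, ( $1.5 \times 10^8$ )—will be administered as per section 5.2.2.1". In 5.4.1.2: "the dose of NSCs ( $1.5 \times 10^8$ ) will then be administered through the Rickham catheter as per section 5.2.2.2". None of the five carries a condition.

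Section 5.3 refers repeat NSC dosing to 5.2.4, which covers 5-FC. The Rickham infusion doses are in 5.2.5.

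**The concern.** In a 3+3 trial, the rules exist mainly for the case where a level fails. That is the case in which these texts part. If level 3 has two or more DLTs, the table takes the level 2 NSC dose into level 4, while the surgical and infusion instructions still call for the level 3 dose that the rule has just rejected. If level 2 fails, they call for a dose that was never opened.

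The excess would be given with leucovorin, which section 6.2.3.3 says can enhance 5-FU toxicity. The 28-day stagger between patients (5.6.4, 7.2) covers levels 1 to 3 only, so an error at level 4 could reach more than one patient before any DLT is read.

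Level 4 is also the only cohort that receives leucovorin and undergoes microdialysis. The primary objective is the phase II dose of the combination with leucovorin, and a secondary objective is PK at the MTD or MFD. If the administration text were followed after a failure, the level 4 DLT rate and PK data would describe a dose other than the one the table defines.

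**Working it through.** The plan states no figure for this point. Its nearest one, in 13.1, is the chance of seeing a toxicity with true rate 0.25 among 6 patients. It reproduces (1 − 0.75^6 = 0.822, stated as about 82%), but nothing below depends on it.

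**Step 1: the texts side by side.**

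| Place | Level 4 NSC dose | Condition |
|---|---|---|
| 5.1 and 5.7 tables, footnote b | highest tolerated | depends on levels 1 to 3 |
| 5.6 | 1.5 × 10^8, as MFD | MTD not reached |
| 5.2.2.1, 5.2.2.2, 5.2.5 | that of level 3 | none |
| 5.4.1.1, 5.4.1.2 | 1.5 × 10^8 | none |

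The same three dose lists in 5.2.2.1, 5.2.2.2 and 5.2.5 attach an explicit condition to level −1. The authors therefore wrote conditions there when they saw a need, and the level 4 lines have none. Section 2.9 adds leucovorin once NSC escalation is complete. It does not require that level 3 be cleared first.

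**Step 2: size of the excess.** Doses and volumes are those in 5.2.2.1.

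| Outcome | Level 4 by the table | Administration text | Dose ratio | Volume ratio |
|---|---|---|---|---|
| Level 3 tolerated | 1.5 × 10^8 in 2.25 ml | the same | 1 | 1 |
| Level 3 fails, level 2 tolerated | 1 × 10^8 in 1.5 ml | 1.5 × 10^8 in 2.25 ml | 1.5 | 2.25/1.5 = 1.5 |
| Level 2 fails, level 1 tolerated | 5 × 10^7 in 0.75 ml | 1.5 × 10^8 in 2.25 ml | 3 | 2.25/0.75 = 3 |

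**Step 3: how often the texts would conflict.** The documents give no DLT rates, so the true rate p is assumed, with q = 1 − p. A level passes with 0/3 DLTs, or with 1/3 followed by 0/3:

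a = q^3 + 3pq^2 × q^3

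A level that is reached fails with probability 1 − a. With the same p at every level, the chance that level 1 passes and level 2 or 3 then fails is a(1 − a) + a^2(1 − a).

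| p | a | Fails once reached | Level 2 fails + level 3 fails | Conflict |
|---|---|---|---|---|
| 0.05 | 0.973 | 0.027 | 0.026 + 0.025 | 5% |
| 0.10 | 0.906 | 0.094 | 0.085 + 0.077 | 16% |
| 0.20 | 0.709 | 0.291 | 0.207 + 0.146 | 35% |
| 0.30 | 0.494 | 0.506 | 0.250 + 0.124 | 37% |
| 1/3 | 0.428 | 0.572 | 0.245 + 0.105 | 35% |

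Rates that rise with dose are more plausible. The chance is then a1(1 − a2) + a1·a2(1 − a3), where the subscript is the level:

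- 5/10/15% at levels 1/2/3: 26%.
- 10/20/30%: 0.906 × 0.291 + 0.906 × 0.709 × 0.506 = 0.264 + 0.325, or 59%.
- 15/25/40%: 0.326 + 0.337, or 66%.

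Cohorts added after a de-escalation are ignored.

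**The case against.** The case for leniency is that the intent is clear and several controls stand between the wording and a patient. Section 4.4 points to 5.7, and every copy of the table says the same thing. Sections 2.9, 5.6 and 9.2 place the microdialysis patients at the MTD or MFD. Under 7.2, "A decision to escalate to the next dose level will be made by the PMT" (the Protocol Management Team), with doses tracked in a log. Under 12.2.3 the drug service must not release agent that would cause a deviation without the principal investigator's approval, and takes ambiguous points to the principal investigator. Sections 5.4.1.1 and 5.4.1.2 also defer to 5.2.2.1 and 5.2.2.2, so the five places are not fully independent. The prior human experience is favourable: section 6.2.2 reports no grade 3 or 4 toxicity attributed to the NSCs. If true DLT rates are 5% to 10%, the texts conflict in 5% to 16% of trials.

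Much of this stands. The table probably shows the intent, the 3+3 design itself is coherent, and the chance of an actual misdose has not been estimated and should be well below the figures above. Two things do not follow. The earlier study gave a single NSC dose of at most 5 × 10^7, so it does not settle the rates at levels 2 and 3 with repeat dosing. And the route through 12.2.3 helps only a reader who notices an ambiguity. A neurosurgeon or cell preparation team working from 5.2.2.1 or 5.4.1.1 alone finds a plain dose and volume.

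**Conclusion.** The concern holds. Five administration instructions fix level 4 at 1.5 × 10^8 NSCs without condition, the dose tables make it depend on what was tolerated, and no section reconciles the two. If level 3 fails, the administration text is 1.5 times the dose the table defines; if level 2 fails, it is 3 times. If level 3 is tolerated, there is no effect.

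The dose ratios come straight from the protocol. The conflict probabilities (5% to 37% with equal rates, 26% to 66% in the rising scenarios) rest on assumed DLT rates and measure disagreement between texts, not misdosing. The safeguards make an error less likely but leave the contradiction in place. It concerns an intracerebral dose in the cohort that answers the primary objective, so the text should be corrected.

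**What to change.** - In 5.2.2.1, 5.2.2.2, 5.2.5, 5.4.1.1 and 5.4.1.2, replace the reference to level 3 and the printed 1.5 × 10^8 with: *the highest tolerated NSC dose per section 5.7, prepared and infused as for that dose level*.
- In 5.3, change the NSC cross-reference from 5.2.4 to 5.2.5, so that repeat cycles follow the corrected text.

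Two clerical slips can be corrected in the same amendment; the conclusion does not rest on them:

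- For days 18–24, the Experimental Design Schema and section 5.1 give 5-FC as 37.5 mg. This should be 37.5 mg/kg, as the dose table referenced in 5.2.7 and 5.3 shows.
- Section 8.2.10 gives leucovorin once daily. It should be 25 mg every 6 hours, as in 2.6.3 and the dose tables.

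The cost is a protocol wording amendment. It adds no patients, visits or procedures.
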